#### 7.3.2 Collection of primary outcome data

Because there is no practical alternative, patient enrolment will take place without prior consent. We will therefore approach patients once they regain a capacity (or a consultee if they do not regain capacity following transfer to a general hospital ward) to inform them of the trial and seek their consent to continue in the study with associated options for further data collection. However, the patient cannot decline to participate in the trial since they have already been randomised and received the trial intervention. We will seek the agreement of CAG to process all data collected up to the point that a participant is approached for consent, and also the primary outcome for all enrolled patients, without their consent. The justification for this is that whilst deceased patients cannot withdraw their data from the study, if those who survive are allowed to withdraw it will create a risk of substantial bias whereby survivors may preferentially withdraw from the study preventing evidence of significant clinical benefit from being detected. In this case we argue that the public interest in completing this research for future patient benefit outweighs the associated breach of confidence.

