### **1.5** Ethical considerations

The trial will be conducted in full conformance with the principles of the Declaration of Helsinki and Good Clinical Practice (GCP) guidelines. It will also comply with all applicable UK legislation including the Mental Capacity Act 2005 and the National Health Service Act 2006 as well as Warwick Standard Operating Procedures (SOPs). All data will be stored securely and held in accordance with the UK General Data Protection Regulation (UK GDPR).

This trial raises several important ethical issues, which have been considered carefully in the development of this protocol, drawing on the relevant legal and regulatory frameworks and previous experience from successful trials in cardiac arrest, involvement in the Health Research Authority Forum on Consent in Emergency Research, and detailed consultation with patients and the public.

The immediately incapacitating nature of cardiac arrest (sudden loss of consciousness) means that it will not be possible to obtain prospective informed consent from participants. Because of the need for immediate treatment, it will also not be possible to obtain an opinion from a personal or professional consultee. Using the provisions within the Mental Capacity Act 2005 Section 32, approval from a Research Ethics Committee to enrol patients without prior consent will be sought. If the patient survives the initial event, and once they have recovered sufficiently (usually once they are recovering on a general hospital ward), a member of the hospital research team will approach the patient (or if they lack capacity, a consultee) whilst they are still in hospital. They will explain the study and seek consent to continue in the trial. However, differential agreement to participate in follow-up arising from early differences in mortality could introduce bias. To avoid this, and ensure 100% data ascertainment of the primary outcome (modified Rankin Scale Score at hospital discharge, or 30 days if the patient remains in hospital at this time), the primary outcome will be collected for all enrolled patients from routinely available data collected locally and by the National Cardiac Arrest Audit with the prior permission of the Health Research Authority Confidentiality Advisory Group (CAG).

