#### 2.3.1 Efficacy

Primary: Modified Rankin Scale (mRS) score assessed at hospital discharge (or at 30 days post-randomisation if the participant remains in hospital).

Secondary:

• Initial ventilation success (visible chest rise with end tidal carbon dioxide monitoring consistent with successful ventilation (where measured) immediately after insertion of a supraglottic airway device or tracheal tube;

• Regurgitation during the resuscitation attempt (stomach contents seen in the patient's pharynx, mouth or nose), and whether this occurred before, during or after advanced airway management;

• Aspiration during the resuscitation attempt (stomach contents seen below the vocal cords, inside a correctly placed tracheal tube or the airway channel of a correctly placed supraglottic airway device), and whether this occurred before, during or after advanced airway management;

- Return of spontaneous circulation (ROSC) for at least 20 minutes;
- Intensive Care Unit length of stay;
- Hospital length of stay;
- Survival to hospital discharge, 3 and 6 months;
- Functional outcome (mRS) score at 3 and 6 months;

• Health-related quality of life at discharge or 30 days (whichever occurs sooner), 3 and 6 months.

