#### 2.7.3 Approaching patients or their consultee following discharge

In rare circumstances, participant consent or a personal/ professional consultee opinion may not be obtained before hospital discharge.

If this occurs, a researcher at the hospital site from which the patient was discharged will contact the participant or their consultee (if it is known that the participant lacks mental capacity) at their home address to seek consent or an opinion. Where possible, the initial contact will be made by post or email to allow time for the patient or consultee to consider their willingness to be contacted. This will be followed by a phone call and second contact if no reply is received. Up to three contact attempts will be made within 28 days of the first contact. The researcher will use available systems to determine correct contact information and, where appropriate, to ensure the participant is still alive. Where available, more than one system will be accessed to determine survival status.

If the participant or their consultee does not respond to this contact within 28 days of the first contact, then we will assume that they do not agree to collection of further routine data or patient-reported outcome measures. We will include only data collected up to that point in the study analysis.

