#### 2.8.2 Post-randomisation withdrawals, exclusions and moves out of region

Post randomisation exclusions may be authorised by the trial management group and approved by the Trial Steering Committee if a participant is randomised in error. However, if a participant is randomised and later found to be ineligible they will still be included in the trial and analysed under the principle of "intention to treat". Similarly, patients who are randomised but do not receive the allocated intervention (for example they achieve a return of spontaneous circulation (ROSC) after randomisation but before advanced airway management is attempted) will be retained and analysed in the group to which they were assigned. In making any decision to exclude after randomisation care will be taken to avoid introducing bias (42).

Participants may cease trial follow-up at any time without prejudice. Unless a participant who has previously consented to continuing data collection explicitly ceases their participation, they should be followed-up wherever possible and data collected as per the protocol until the end of the trial.

If at any point following consent the patient (or their consultee) indicates that they no longer wish to participate usual care will continue to be provided. This will be logged on the database from the point they cease participation, and no further contact will be made. All non-identifiable data collected up to that point will be retained and included in the analysis. If the patient (or their consultee) indicates that they wish to be withdrawn from the study, no further data will be collected and no further contact will be made. All non-identifiable data collected prior to consent and the primary outcome will be retained and included in the analysis.

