# 6.2 Statistical analysis of efficacy and harms

#### 6.2.1 Statistics and data analysis

The primary statistical analysis will be by intention to treat amongst those randomised to TI versus SGA. The primary outcome rate will be assessed using a mixed-effects logistic regression model with hospital site as a random effect and adjustment for pre-defined important fixed covariates. These

covariates will be included in the analysis plan, prior to any analysis. Secondary outcomes which are categorical will be analysed in a similar way (using mixed-effects logistic regression models). For continuous outcomes, we will assess the distribution of the data and use appropriate analytical methods – if the data is normally distributed we will use mixed-effects linear regression models and if it is non-normal we will use log transform of the data or the gamma distribution to model the data. Results will be reported using odds ratio or mean difference with 95% confidence intervals.

Crossover: Crossover will be assessed in two ways:

(i) impact on the statistical power of the study: due to the contamination effect in patients who crossover from one intervention to another, there is likely to be a reduction in the study power. We will examine the loss of power, using power curves and different degrees of crossover, pivoted around the observed crossover rates(38), and assess this at the end of the pilot study as well as presenting these to the DMC at each 6-monthly analysis.

(ii) for the final analysis, we will use inverse probability weighted (IPW) analysis to account for crossovers, using the primary outcome measure.

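### Data sought without consent stop at the primary outcome, so some UK survivors will have no vital status at 3 and 6 months while earlier deaths are kept

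*Protocol*

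**What the plan says.** Survival at later time points is a named secondary outcome in Protocol section 2.3.1: "Survival to hospital discharge, 3 and 6 months". Section 6.2.3.3 takes it from the national audit, site data and hospital episode records, and notes that it belongs to the cardiac arrest core outcome set.

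Section 7.3.2 sets what may be held without consent. It covers data up to the approach ("We will seek the agreement of CAG to process all data collected up to the point that a participant is approached for consent") and then "and also the primary outcome for all enrolled patients, without their consent". The reason it gives, a concern about bias, begins: "whilst deceased patients cannot withdraw their data from the study, if those who survive are allowed to withdraw it will create a risk of substantial". Section 1.5 makes the same point about follow-up: "differential agreement to participate in follow-up arising from early differences in mortality could introduce bias".

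Three routes end data collection for a survivor:

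- Option (a) of the three consent options in section 2.7.2, which ends participation. Option (b) keeps routine data and drops only contact and questionnaires.
- Withdrawal under section 2.8.2: if the patient or consultee "indicates that they wish to be withdrawn from the study, no further data will be collected". Data from before consent and the primary outcome are kept.
- No reply within 28 days to the consent approach made after discharge (section 2.7.3): "then we will assume that they do not agree to collection of further routine data or patient-reported outcome measures".

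Section 7.3.1 seeks a defined data set for the deceased without consent. On analysis, section 6.2.1 says: "Secondary outcomes which are categorical will be analysed in a similar way (using mixed-effects logistic regression models"), with results given as odds ratios or mean differences.

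**The concern.** The argument used to protect the primary outcome applies equally to survival at 3 and 6 months, yet that outcome is not covered. In the UK, a patient who dies before the approach is always counted. A patient alive at the approach who leaves by one of the three routes is not. Missing vital status is thus confined to people who had survived so far, and missingness depends on the outcome being measured.

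At stake are the absolute 3- and 6-month survival proportions, which also matter because 6-month outcomes and prognosis feed the lifetime economic model (section 6.6). The treatment effect on survival is at stake too if the loss differs between arms. An analysis plan cannot recover a status that was never collected, so the gap lies in the scope of the data request, which the protocol fixes.

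**Working it through.** **Inputs.** From section 6.1: 8.5% v 11.5%, 2,095 per arm, 5% level, 90% power. These rates were set from mortality data, so they can stand in for survival. I take the lower rate as tracheal intubation (TI) and the higher as the supraglottic airway (SGA), following the superiority hypothesis in section 1.3, and treat the test as two-sided. The share f of survivors with lost status is **an assumption**, because the protocol gives no refusal or non-reply rate.

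**The plan's own figure.** The two-proportion formula gives 4,200 in total with pooled variance and 4,194 unpooled, against 4,190 stated. Power at 2,095 per arm is 89.9%. The figure reproduces.

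**Formulas.** If a share f of survivors is lost and all deaths are kept, survival among patients with recorded status is

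q = p(1 − f) / (1 − pf).

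The observed odds are p(1 − f)/(1 − p), so

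observed OR = true OR × (1 − f_SGA)/(1 − f_TI).

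The true OR is (0.115/0.885)/(0.085/0.915) = 1.399. Equal loss cancels.

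**Example, f = 10% in both arms.** TI: 0.0765/0.9915 = 7.72%. SGA: 0.1035/0.9885 = 10.47%. Difference 2.75 points. About 42 patients are lost: 2,095 × (0.085 + 0.115) × 0.10.

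| Assumed loss TI / SGA | Observed survival TI v SGA | Difference (points) | OR | Power |
|---|---|---|---|---|
| 0 / 0 | 8.50% v 11.50% | 3.00 | 1.399 | 89.9% |
| 2% / 2% | 8.34% v 11.30% | 2.95 | 1.399 | 89.4% |
| 5% / 5% | 8.11% v 10.99% | 2.88 | 1.399 | 88.6% |
| 10% / 10% | 7.72% v 10.47% | 2.75 | 1.399 | 87.0% |
| 20% / 20% | 6.92% v 9.42% | 2.50 | 1.399 | 83.3% |
| 5% / 10% | 8.11% v 10.47% | 2.36 | 1.325 | 74.6% |
| 5% / 15% | 8.11% v 9.95% | 1.84 | 1.252 | 54% |
| 20% / 10% | 6.92% v 10.47% | 3.55 | 1.574 | 98.2% |

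**No true difference (10% in both arms).** Loss of 5% v 15% gives 9.55% v 8.63%, a false difference of −0.92 points and OR 0.85/0.95 = 0.895. The two-sided 5% test then rejects in about 18% of trials. Loss of 2% v 4% gives −0.18 points, OR 0.96/0.98 = 0.98 and rejection of about 5.4%, which is close to nominal.

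**Later deaths.** Lost patients are known to be alive only at the approach. If 10% to 20% of survivors die afterwards, equal losses of 10% to 20% move the odds ratio by no more than 0.002 (for example 1.3907 observed against 1.3887 true).

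**The case against.** Much of the opposing case stands.

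- **Effect measure.** For a binary outcome, section 6.2.1 points to the odds ratio. Equal loss leaves it unchanged, so the shrinking absolute difference is not bias in the planned effect estimate. A reader might infer that the treatment effect is pulled towards zero whenever survivors are lost; the arithmetic does not support that.
- **Size of the loss.** Section 2.7.2 reports high levels of consent to continue in previous trials using this approach. Section 2.7.3 calls consent not obtained before discharge rare, and the 28-day rule applies only to that group. The follow-up rate above 98% in section 3.2.3 concerns contact for follow-up in previous studies, so it does not measure refusal, but nothing in the protocol suggests heavy loss.
- **Who is lost.** A reader might infer that everyone who declines or fails to respond drops out. That is too broad. Option (b) patients keep routine data and can be counted for survival, as can consented patients who leave a questionnaire unanswered.
- **Unequal loss.** Section 2.10.1 says patients are blinded and sites are encouraged not to disclose the allocation, which makes a large difference in refusal less likely. The 5% v 15% example is illustrative. Blinding is only encouraged, however, and the concern in section 1.5 rests on early mortality differences, so it needs no knowledge of allocation.
- **Analysis.** Section 6.2.1 names a model without prescribing complete cases. Missing-data handling may sit in an analysis plan that is not shown, so its absence here is no fault.
- **Finland.** Under Appendix A, consent is also sought from next of kin after a death, so it is not certain that all earlier deaths are kept there.
- **Ethics.** Holding vital status against an explicit refusal is a judgement for CAG, not a statistical error.

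What remains is the scope of the request. For UK patients leaving by the three routes, later vital status is never collected, on grounds that section 7.3.2 itself treats as a source of bias.

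**Conclusion.** The concern holds in a limited form and is minor. The primary outcome is unaffected. Survival to discharge is largely covered, because death by discharge or day 30 is part of the primary outcome; only non-consenting patients still in hospital at day 30 are exposed.

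For 3- and 6-month survival, an analysis restricted to recorded status would understate survival in both arms and reduce the absolute difference by about 0.25 points per 10% of survivors lost. Under equal loss the odds ratio is essentially unchanged and the cost is some power. It is biased, in either direction, only if loss differs by arm: clearly at 5% v 15%, and hardly at 2% v 4% when there is no true effect. All these sizes rest on assumed loss rates and on survival close to the sample-size rates. The protocol's indications are that losses will be low.

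**What to change.** 1. In section 7.3.2, ask CAG to include vital status (date of death) to 6 months for enrolled UK participants, on the justification already given for the primary outcome. At the least, cover those who never replied to the consent approach, and leave to CAG whether it extends to explicit refusals. Align sections 2.7.3 and 2.8.2 with the outcome.
2. Where status stays unavailable, keep all randomised patients in the 3- and 6-month survival analysis. Censor decliners and non-repliers at the date last known alive and estimate survival by arm with time-to-event methods. Report refusals and non-replies by arm, with a sensitivity analysis over the unknown statuses.

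The cost is one more item in the CAG request, matching participant-information wording and a small change of method, with no extra patients or visits. The downsides are that one more item is processed without consent, which CAG may refuse, and that censoring assumes these patients go on to survive like those who consented.

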#### 7.3.3 National data opt out

The national data opt out requires that patients who have previously indicated that they do not wish their data to be used for research are not included in research studies, unless they expressly give their consent to do so. This trial enrols participants without prior consent, and there is also no

opportunity to confirm the patient's national data opt out status prior to enrolment. As a result, we anticipate that we will inadvertently enrol patients who have a national data opt out in place.

Following consultation with our PPI advisors, we propose to withdraw from the study all patients who have registered a national data opt out as soon as possible after enrolment. Only a record of the total number of patients withdrawn from each arm for this reason will be retained to comply with the conventions of CONSORT trial reporting and confirm that the proportion of patients with a national data opt out is the same in the two trial groups. However, we cannot allow patients who have survived to preferentially "opt in" to the trial subsequently, because this may introduce significant bias to the results. Our PPI advisors have therefore recommended that we do not approach survivors who have registered a national data opt out, since we will have withdrawn them in keeping with their previously expressed wishes, we cannot offer them an option to participate and the additional burden of this information, when recovering from a life-threatening illness, is of no benefit to the individual. We will be informing any patients who have opted out of any SAE occurrence.

#### 7.4 Trial Registration

The AIRWAYS-3 trial will be registered with the International Standard Registered Clinical/soCial sTudy Number (ISRCTN) Register.

#### 7.5 Notification of serious breaches to GCP and/or trial protocol

A "serious breach" is a breach which is likely to effect to a significant degree:

- (a) the safety or physical or mental integrity of the subjects of the trial; or
- (b) the scientific value of the trial

The sponsor will be notified immediately of any case where the above definition applies during the trial conduct phase.

#### 7.6 Indemnity

The AIRWAYS-3 trial is sponsored by University Hospitals Bristol and Weston NHS Foundation Trust, co-sponsored by University of Warwick (for sites outside of the UK) and co-ordinated by the Warwick CTU in the University of Warwick. The trial will be conducted in accordance with Warwick Clinical Trial Unit Standard Operating procedures.

#### Sponsor: UK only

University Hospitals Bristol and Weston NHS Foundation Trust

This is an NHS-sponsored research study. If there is negligent harm during the clinical trial when the NHS body owes a duty of care to the person harmed, NHS Indemnity covers NHS staff, medical academic staff with honorary contracts, and those conducting the trial. NHS Indemnity does not offer no-fault compensation and is unable to agree in advance to pay compensation for non-negligent harm. Ex-gratia payments may be considered in the case of a claim. All sites, UK and International, should ensure that they carry insurance allowing them to conduct studies including this one.

#### Co-Sponsor: Non-UK International sites only

The University of Warwick will provide insurance cover in relation to the International sites

Equivalent cover to that provided by the Clinical Negligence Scheme for UK Trusts should be confirmed to be in place for non-UK sites during site suitability assessment and this cover must be summarised in the sponsor-site contract.

# 7.7 Trial timetable and milestones

PROJECT ACTIVITY (RANGE OF MONTHS)	1 TO 9	10 TO 15	16 TO 21	22 TO 27	28 TO 33	34 TO 38	39 TO 40	41 TO 42	43 TO 48
PROJECT ACTIVITY (48 MONTHS)	9	6	6	6	6	6	2	1	6
STAGE OF TRIAL	set-up	pilot	main trial	main trial	main trial	follow-up	follow-up	analysis	reporting
site set-up									
training initiated									
Ethincs regulatory approvals									
Final protocol/draft CRFs									
Set up processes for NCAA data									
START OF PILOT									
sites open		40							
patient recruitment		*							
3 month follow-up		*							
6 month follow-up		*							
MAIN TRIAL									
sites open (cumulative)			100	120	120				
patient recruitment			*	*	*				
3 month follow-up				*	*	*	*		
6 month follow-up				*	*	*	*		
TRIAL MANAGEMENT/REPORTING									
data processing	Prep								
data analysis	prep								
TMG meetings	****	****	****	****	****	****	****	****	
TSC meetings	*	*	*	*	*	*			
DMeC meetings	*	*	*	*	*	*			*
PPI Panel meetings	***	***	***	***	***	***		***	***
Monitoring report	*	*	*	*	*	*		*	*
Dissemination	*	*	*	*	*	*		*	*
Eligible patients (x 2.1 of randomised)		886	2811	5832	8896				
Patient accrual		420	840	1260	1680				
Patient accrual (cumulative)		420	1332	2764	4216				

#### 7.8 Administration

The study will be coordinated by the Warwick CTU (WCTU) which has specific expertise in undertaking studies in emergency and critical care. The study will be conducted according to defined Warwick SOPs.

The WCTU will be responsible for protocol development, ethics and governance approvals, database development and data management, randomisation, trial management and monitoring, analysis of the data and reporting.

The study will be monitored in accordance with Warwick Monitoring SOP. All study related documents will be made available on request for monitoring and audit by Warwick CTU, the Sponsor, the relevant Research Ethics Committee and for any other regulatory authorities.

